3.4.2.2. Systemic Events

The systemic events reported in the e-diary after each vaccination are decreased appetite, drowsiness, and irritability (for Cohorts 2 and 3) and fatigue, headache, vomiting, diarrhea, muscle pain, and joint pain (for Cohort 4). These will be recorded as present or absent. Fever and use of antipyretic medication will also be included as systemic events.

PFIZER CONFIDENTIAL
Page 14

3.4.2.2.1. Fever: Cohorts 2, 3 and 4

The subject's axillary temperature will be recorded in the e-diary for 7 days (Day 1 to Day 7) after each vaccination. If more than 1 temperature was taken for a subject on the same day, the highest temperature was to be recorded in the e-diary.

The protocol defines fever as a temperature $\geq 38.0^{\circ}$ C (or $\geq 100.4^{\circ}$ F). In the event of a fever, temperature will be taken daily until fever has resolved (1 day of temperature less than 38.0°C [100.4°F]). An end date will be captured in the CRF for any fever persisting on the last day that the e-diary was completed.

Fever will be classified as following for a given day based on the following scale:

- = •, if temperature is missing, or otherwise unavailable;
- = 0 (absent), if temperature is not missing and $<38.0^{\circ}C$ (100.4°F);
- = 1 (mild), if temperature is ≥38.0°C (100.4°F) but ≤39.0°C (102.2°F);
- = 2 (moderate), if temperature is >39.0°C (102.2°F) but ≤40°C (104.0°F);
- = 3 (severe), if temperature is >40.0°C (104.0°F).

In addition, following the guidelines published by China State Food and Drug Administration (SFDA), fever will be also classified for a given day defined by China SFDA based on the following scale:

- = •, if temperature is missing, <35.0°C (95.0°F), >42.0°C (107.6°F), or otherwise unavailable;
- = 0 (absent), if temperature is not missing and <37.1°C (98.8°F);
- = 1 (mild), if temperature is ≥37.1°C (98.8°F) but <37.6°C (99.7°F);
- = 2 (moderate), if temperature is ≥37.6°C (99.7°F) but ≤39.0°C (102.2°F);
- = 3 (severe), if temperature is $>39.0^{\circ}$ C (102.2°F).

Similar to the derivations specified for local reactions, any day, any fever, any fever on any day, and duration of fever will be derived. Duration will be calculated for any fever (temperature $\geq 38.0^{\circ}$ C [$\geq 100.4^{\circ}$ F]) and for any fever (temperature $\geq 37.1^{\circ}$ C [$\geq 98.8^{\circ}$ F]). Each category of fever will be included as a separate event in summaries of systemic events.

3.4.2.2.2. Other Systemic Events: Cohorts 2, 3, and 4

The presence of systemic events will be recorded in the e-diary daily for 7 days (Day 1 to Day 7) after each vaccination, using the grading scales in Table 8 and Table 9.

Systemic Event	GRADE 1	GRADE 2	GRADE 3	GRADE 4 ^a
	mild	moderate	severe	
Decreased appetite (Loss of appetite)	Decreased interest in eating	Decreased oral intake	Refusal to feed	Emergency room visit or hospitalization for severe loss of appetite
Drowsiness (increased sleep)	Increased or prolonged sleeping bouts	Slightly subdued interfering with daily activity	Disabling not interested in usual daily activity	Emergency room visit or hospitalization or severe increased sleep
Irritability (fussiness) (synonymous with restless sleep; decreased sleep)	Easily consolable	Requiring increased attention	Inconsolable; crying cannot be comforted	Emergency room visit or hospitalization for severe irritability

Table 8.Other Systemic Events for Infants Aged 7 Months to <2 Years
(Cohort 2 and 3)

a. Grade 4 assessment should be made by an investigator; Grade 4 will not be collected in the e-diary but as an adverse event on the case report form.

Table 9.	Other Systemic Ev	ents for Children A	Aged ≥ 2 to <6 Years (Cohort 4)
----------	-------------------	---------------------	-----------------------------	-----------

Systemic Event	GRADE 1 mild	GRADE 2 moderate	GRADE 3 severe	GRADE 4 ^a
Fatigue (= tiredness in e-diaries)	Does not interfere with activity	Some interference with activity	Prevents daily routine activity	Emergency room visit or hospitalization for severe fatigue
Headache	Does not interfere with activity	Some interference with activity	Prevents daily routine activity	Emergency room visit or hospitalization for severe headache
Vomiting	1 to 2 times in 24 hours	>2 times in 24 hours	Requires intravenous hydration	Emergency room visit or hospitalization for severe vomiting
Diarrhea	2 to 3 loose stools in 24 hours	4 to 5 loose stools in 24 hours	6 or more loose stools in 24 hours	Emergency room visit or hospitalization for severe diarrhea

Systemic Event	GRADE 1 mild	GRADE 2 moderate	GRADE 3 severe	GRADE 4 ^a
Muscle pain	Does not interfere with activity	Some interference with activity	Prevents daily routine activity	Emergency room visit or hospitalization for severe muscle pain
Joint pain	Does not interfere with activity	Some interference with activity	Prevents daily routine activity	Emergency room visit or hospitalization for severe joint pain

Table 9. Other Systemic Events for Children Aged ≥ 2 to <6 Years (Cohort 4)

a. Grade 4 assessment should be made by an investigator; Grade 4 will not be collected in the e-diary but as an adverse event on the case report form.

For decreased appetite or loss of appetite on each day, an indicator variable will be created for decreased appetite on each day, using the following algorithm:

- = •, if decreased appetite is missing;
- = 0 (none), if no loss of appetite;
- = 1 (mild), if decreased interest in eating;
- = 2 (moderate), if decreased oral intake;
- = 3 (severe), if refusal to feed.

For drowsiness (synonym with increased sleep) on each day, an indicator variable will be created for drowsiness on each day, using the following algorithm:

- = •, if increased sleep is missing;
- = 0 (none), if no synonym with increased sleep;
- = 1 (mild), if increased or prolonged sleeping bouts;
- = 2 (moderate), if slightly subdued; interfering with daily activity;
- = 3 (severe), if disabling; not interested in usual daily activity.

For irritability (fussiness, synonym with restless sleep; decreased sleep) on each day, an indicator variable will be created for irritability on each day, using the following algorithm:

- = •, if irritability is missing;
- = 0 (none), if no fussiness;
- = 1 (mild), if easily consolable;
- = 2 (moderate), if requiring increased attention;

= 3 (severe), if inconsolable; crying that cannot be comforted.

For fatigue (synonym with tiredness in e-diaries), headache, muscle pain, and joint pain on each day, an indicator variable will be created for them on each day separately, using the following algorithm:

- = •, if fatigue, headache, muscle pain, or joint pain is missing;
- = 0 (none), if no fatigue, headache, muscle pain, or joint pain;
- = 1 (mild), if does not interfere with activity;
- = 2 (moderate), if some interference with activity;
- = 3 (severe), if prevents daily routine activity.

For vomiting on each day, an indicator variable will be created on each day using the following algorithm:

- = •, if vomiting is missing;
- = 0 (none), if no vomiting;
- = 1 (mild), if 1 to 2 times in 24 hours;
- = 2 (moderate), if > 2 times in 24 hours;
- = 3 (severe), if requires intravenous hydration.

For diarrhea on each day, an indicator variable will be created on each day using the following algorithm:

- = •, if diarrhea is missing;
- = 0 (none), if no diarrhea;
- = 1 (mild), if 2 to 3 loose stools in 24 hours;
- = 2 (moderate), if 4 to 5 loose stools in 24 hours;
- = 3 (severe), if 6 or more loose stools in 24 hours.

For the systemic events, 3 more derivations are required: whether or not a specific reaction occurs on any day, whether or not the subject experiences any other systemic event on a given day, and whether or not the subject experiences any other systemic events on any day; similar algorithms described in Section 3.4.2.1 will be used.

3.4.2.2.3. Use of Antipyretic Medication

The caregiver will be instructed to record the use of antipyretic medications for prevention or treatment of symptoms daily during the active safety observation periods (Day 1 to Day 7) after each vaccination and record the information in the e-diary.

PFIZER CONFIDENTIAL	
Page 18	

An end date will be collected in the CRF for any antipyretic medication use persisting on the last day that the e-diary was completed. Data on the use of other concomitant medication will not be collected.

Similar to the derivation specified for local reactions, "any day" (for data from Day 1 to Day 7), "any medication" (for data from Day 1 to Day 7), "any medication on any day" (for data from Day 1 to Day 7) and duration will be derived for use of antipyretic medications. The same algorithms as specified in Section 3.4.2.1 will be used.

3.4.3. Hospitalization

Hospitalization information will be captured in the SAE form, including dates of admission, discharge, and whether continuing.

3.4.4. Death

Date and cause of death will be captured in the CRF. Subjects narratives will be produced for subjects with SAEs leading to outcome of death.

3.5. Study Conduct

3.5.1. E-Diary Completion

An e-diary will be considered transmitted if any data for the local reactions and the systemic events are present on any day. If all data are missing for all items on the e-diary for all 7 days following vaccination, then the e-diary will be considered not transmitted.

For transmitted e-diaries, the following variables will be defined: "Day 1," "Day 2," "Day 3," "Day 4," "Day 5," "Day 6," "Day 7," "Day 1 – Day 7".

An e-diary will be considered completed if all expected data for all 7 days are available (ie, not missing) and data are valid. Otherwise, the e-diary will be considered incomplete.

For any given day, an e-diary will be considered complete if all expected data are available.

For completed e-diaries, the following variables will be defined: "Day 1," "Day 2," "Day 3," "Day 4," "Day 5," "Day 6," "Day 7," "Day 1 – Day 7".

For e-diaries that are incomplete, an indicator variable for the percentage of days without data will be derived as follows:

- = 1, if data have been transmitted, and are complete for 7 days (100%);
- = 2, if data have been transmitted, and are complete for 6 days (\geq 75% to <100%);
- = 3, if data have been transmitted, and are complete for 4 or 5 days (\geq 50% to <75%);
- = 4, if data have been transmitted, and are complete for 2 or 3 days ($\geq 25\%$ to <50%);
- = 5, if data have been transmitted, and are complete for 0 or 1 day (<25%).

3.5.2. Demographic, Medical History, and Baseline Characteristics Variables

The demographic variables are age at randomization/first vaccination visit (in month) at Visit 1, sex, race, and ethnicity. Age will be calculated as $12 \times (randomization/first vaccination date - date of birth + 1)/365.25$ and rounded to 1 decimal place.

Medical history will be categorized according to MedDRA.

Clinically significant findings for physical examination will be recorded as yes or no in the CRF.

3.5.3. Nonstudy Vaccines and Medications

Nonstudy vaccines and concomitant medications will be categorized according to the World Health Organization (WHO) Drug Dictionary (WHODD).

3.5.3.1. Prior Treatment

Details of any medication or vaccines received prior to enrollment into the study will not be collected in the CRF.

3.5.3.2. Concomitant Vaccines and Medication(s)

The name and date of administration of any nonstudy vaccines given from the time of signing the ICD until 6 months after the last vaccination visit will be recorded in the CRF. Other medications (except for antipyretic medication use) will not be recorded in the CRF. Antipyretic medication taken will be reported in the subject's e-diary and stop date recorded in the e-diary/CRF (as part of the symptoms resolved dates CRF).

3.5.3.3. Permitted Vaccines

Vaccinations, including Hib vaccination, may be given ≥ 4 days before or ≥ 7 days after study vaccination, except for bacille Calmette-Guérin (BCG) vaccine and oral vaccines, which are allowed at any time, according to local practice or national recommendations, at the discretion of the investigator.

3.5.3.4. Permitted Treatments

- A local anesthetic may be used at the site of the blood draw.
- Topical and inhaled corticosteroids may be used.
- Antipyretic medication may be used; however, prophylactic use should be discouraged.

Haemophilus influenzae Type b Vaccine:

- 13vPnC recipients in Cohort 1, 2, 3 or 4 will be offered Hib vaccinations according to local practice or national recommendations, at the discretion of the investigator. Refer to Section 3.5.3.3 for further details of when Hib vaccine may be given. Investigational sites will be reimbursed for any Hib vaccinations given. Hib vaccinations will be given outside of the study.
- Hib recipients in Cohort 2 will all be offered additional Hib vaccination(s) according to local practice or national recommendations, at the discretion of the investigator. Refer to Section 3.5.3.3 for further details of when Hib vaccine may be given. Investigational sites will be reimbursed for any Hib vaccinations given. Hib vaccinations will be given outside of the study.

4. ANALYSIS SETS

Data for all subjects will be assessed to determine if subjects meet the criteria for inclusion in each analysis population prior to unblinding and releasing the database and classifications will be documented per standard operating procedures.

4.1. Evaluable Analysis Set

One evaluable analysis set will be defined for Cohort 1 infant series and Cohort 2, 3, 4; it will include all subjects who:

- 1. Are eligible for the study at randomization.
- 2. Have received all study vaccinations to which they are randomized for Cohort 2, 3 and 4; received all 3 infant series doses to which they are assigned for cohort 1.
- 3. Have blood drawn for assay testing within the required time frame (27 to 56 days after third vaccination for Cohort 1, 27 to 56 days after visit 3 for Cohort 2, 27 to 56 days after visit 2 for Cohort 3, 27 to 56 days after visit 1 for Cohort 4) and the sample from this blood draw provides at least 1 valid and determinate assay result.
- 4. Receive no prohibited vaccines.
- 5. Have no major protocol violations as determined by the study clinician.

The evaluable immunogenicity population defined for Cohort 1 post-toddler dose will include all subjects who:

- 1. Are eligible for the study.
- 2. Have received all 4 study vaccinations to which they were assigned (3 infant doses and 1 toddler dose).

- 3. Have blood drawn for assay testing within the required time frame (27 to 56 Days after vaccination 4 [Visit 5]) and the sample from this blood draw provides at least 1 valid and determinate assay result.
- 4. Receive no prohibited vaccines before blood draw after the toddler dose.
- 5. Have no major protocol violations as determined by the study clinician.

The evaluable immunogenicity population will be the primary analysis population for all immunogenicity endpoints. The immunogenicity results will be summarized according to the vaccine group as randomly assigned for Cohort 2, 3 and 4.

Subjects vaccinated but not randomized in Cohort 2, 3, 4 and subjects randomized but who receive the wrong vaccine in Cohort 2, 3, 4 will be excluded from the evaluable immunogenicity population.

4.2. All-available Immunogenicity Analysis Set

Separate all-available immunogenicity analysis set will be defined for Cohort 1 infant series, Cohort 2, 3, 4; and also be defined for Cohort 1 toddler dose.

All-available immunogenicity analysis set will include all subjects who have at least 1 valid and determinate assay result for the proposed analysis. This analysis set is for the purpose of immunogenicity analysis, for which it will be secondary analysis population.

Subjects randomized but not vaccinated in Cohort 2, 3, and 4 will be included in the all-available immunogenicity analysis set if any valid and determinate assay results are available.

Subjects vaccinated but not randomized in Cohort 2, 3 and 4 will be excluded from the allavailable immunogenicity analysis set.

4.3. Full Analysis Set

Not applicable.

4.4. Per Protocol Analysis Set

Not applicable.

4.5. Safety Analysis Set

The safety population will include all subjects who receive at least 1 dose of the investigational product. Separate safety populations will be defined for subjects in Cohort 1 with infant dose series and subjects in Cohort 2, 3, 4, and also be defined for subjects in Cohort 1 with toddler dose.

Subjects vaccinated but not randomized in Cohort 2, 3, 4 will be included in the safety population for safety analysis, and results from these subjects will be reported under the group corresponding to the vaccine they actually received.

Subjects who were randomized but received the wrong vaccine in Cohort 2, 3 and 4 will be included in the safety population for safety analysis, and results from these subjects will be reported under the group corresponding to the vaccine they actually received.

4.6. Other Analysis Sets

Not applicable.

5. GENERAL METHODOLOGY AND CONVENTIONS

5.1. Hypotheses and Decision Rules

No formal statistical hypothesis test will be performed as this is a descriptive study and no formal hypotheses were predetermined. There are also no formal statistical decision rules for this study and a descriptive estimation approach will be used to assess all study objectives regarding safety and immunogenicity in the study.

Point estimates and nominal 95% confidence intervals (CIs) will be provided for all safety and immunogenicity endpoints at each planned analysis.

No formal multiplicity adjustments will be applied due to multiple endpoints or multiple looks of the same endpoint.

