9. DATA ANALYSIS/STATISTICAL METHODS

Detailed methodology for summary and statistical analyses of the data collected in this study is outlined here and further detailed in a statistical analysis plan (SAP), which will be maintained by the sponsor. The SAP may modify what is outlined in the protocol where appropriate; however, any major modifications of the primary endpoint definitions or their analyses will also be reflected in a protocol amendment.

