9.2.1. Analysis of the Primary Immunogenicity Endpoint

The study primary objective is to compare the serotype specific IgG GMCs to each of the 13 pneumococcal serotypes induced by 13vPnC between each cohort in the age of 7 months to < 6 years (Cohort 2, Cohort 3, Cohort 4) and infant Cohort 1. For each cohort (Cohort 2, Cohort 3, Cohort 4), the primary objective will be achieved if the non-inferiority criterion is met, or the lower bound of the 95% CI on the geometric mean ratio (GMR) (1 month after the last vaccination of Cohort 2, Cohort 3, Cohort 4 to 1 month after the last vaccination of infant series of Cohort 1) is greater than 0.5 for all 13 serotypes. For each of the 13 serotypes contained in 13vPnC, GMCs will be calculated at 1 month after the last vaccination for Cohort 2, Cohort 4, and 1 month after infant series for Cohort 1, along with 2-sided 95% CIs on the GMCs, which will be constructed by back transformation of the CIs for the mean of the logarithmically transformed IgG computed using Student's t distribution. The 2-sided 95% CIs on the GMRs (GMC 13vPnC in Cohort 2, 3, or 4/GMC 13vPnC in Cohort 1) will be calculated using Student's t distribution for the mean difference of the measures on the natural log (ln) scale.

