9.2.2. Analysis of the Secondary Immunogenicity Endpoint

All secondary immunogenicity endpoints are descriptive and will be summarized by cohort/group, along with point estimates and 95% CIs.

The analyses as described above for primary endpoint will also be repeated for OPA geometric mean titers (GMTs) and geometric mean titer ratios (GMTRs) measured for selected subjects in each cohort.

The proportion of subjects achieving an IgG concentration $\ge 0.35 \ \mu g/mL$, as well as the proportion of subjects with pneumococcal OPA titer above a defined level will be computed for each tested blood sample obtained from subjects in all cohorts, and the proportion differences for each serotype in 13vPnC between 1 month after the last vaccination of each cohort (Cohort 2, Cohort 3, Cohort 4) and 1 month after last vaccination of infant series of Cohort 1, along with associated exact (Clopper-Pearson's) 2-sided 95% CIs will be provided. Within each cohort in the age of 7 months to < 6 years (Cohort 2, Cohort 3, Cohort 4), the GMRs (IgG GMC 13vPnC/GMC Hib vaccine and OPA GMT 13vPnC/GMT Hib vaccine) and associated 2-sided 95% CIs on GMRs produced by a similar approach described in above Section 9.2.1 will be provided; and proportion differences between 13vPnC and Hib, and associated exact 2-sided 95% CIs by Chan and Zhang's method will be provided.

The GMCs and GMTs at each blood draw time point in each cohort will be provided by vaccine group. The geometric mean fold rises (GMFRs) in IgG and OPA from before vaccination to after vaccination at all post baseline blood sampling time points thought 1 month after infant series for Cohort 1, and all post baseline blood sampling time points for Cohort 2, 3 and 4, will be summarized with 2-sided 95% CIs, also computed using the logarithmically transformed assay results. In addition, the GMFRs in IgG and OPA from before toddler dose to after toddler dose at all post toddler dose blood sampling time points for Cohort 1 will be summarized with corresponding 2-sided 95% CIs.

Reverse cumulative distribution curves (RCDCs) will be presented graphically by vaccine group separately for each serotype-specific pneumococcal IgG concentration at each blood draw time point in each cohort.

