9.5. Sample Size Calculation

The type I error for all comparisons between each cohort in the age of 7 months to < 6 years and Cohort 1 (infant) is 5% (or 2.5%, 1-sided test of non-inferiority). As all comparisons between children with age of 7 months to < 6 year and infants are independent of each other, the type I error is not adjusted.

Sample size estimations are based upon GMCs in all Cohorts and data from studies in China (B1841008, and B1851015). The sample size/power estimates for non-inferiority of each Cohort in the age of 7 months to < 6 years relative to the Cohort 1 are evaluated based on following assumptions:

- 1. 2-sided type I error of 5%,
- 2. 2-fold non-inferiority criterion for GMC,
- 3. differences in true GMCs for 7 common serotypes (4, 6B, 9V, 14, 18C, 19F, 23F) between each Cohort in the age of 7 months to < 6 years and the Cohort 1 (infant) are the same as the data observed in study B1841008,
- 4. differences in true GMCs for 6 additional serotypes (1,3,5, 6A, 7F, 19A) between each cohort in the age of 7 months to < 6 years and Cohort 1 are zero and GMCs of these 6 additional serotype for Cohort 1 are the same as 1 month after infant series in Group 3 from study B1851015.

This assumption (d) may be conservative as actually better GMCs in the children of 7 months to <6 years for these 6 additional serotypes were observed when compared GMCs between 1 month after last dose in the age of 7 months to <6 years and 1 month after infant series in the studies performed in Poland (6096A1-3000 and 6096A1-3002).

The sample size estimations for non-inferiority of 13vPnC in the Cohort 2 (age 7 months to < 12 months) relative to 13vPnC in the Cohort 1 are presented in Table 12. Non-inferiority assumptions are as stated above, the 7vPnC data for Cohort 1 were based on GMC results of 1 month after infant series in Group 1 of study B1841008, and 7vPnC data for Cohort 2 were based on GMC results of 1 month after last vaccination of Group 2 in study B1841008. With a 2:1 randomization ratio (13vPnC : Hib vaccine) in the Cohort 2, a total of 150 evaluable subjects will provide 100 evaluable subjects with 13vPnC and therefore provide more than 90% power to declare non-inferiority relative to Cohort 1 across all 13 serotypes. With about 15% of randomized subjects nonevaluable in the Cohort 2, the total number of subjects to be randomized in Cohort 2 will be 177.

	Co	hort 1(13vP	nC)	Co	hort 2(13vP	nC)	Differenc	Common	Power N= 200 (100:100)

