6A	4.76	1.560	0.994				0	0.994	0.998
7F	8.28	2.114	0.778				0	0.778	>0.999
19A	5.1	1.629	0.928				0	0.928	>0.999
Overall									0.995

Table 13.Power Estimates for Cohort 3, Based on Geometric Mean ConcentrationFrom Studies B1841008 and B1851015

Abbreviations: GMC = geometric mean concentration; SD = standard deviation. LOG= natural logarithm.

The sample size estimations for non-inferiority of 13vPnC in Cohort 4 (age 2 to < 6 years) relative to Cohort 1 (infant) are presented in Table 14. Non-inferiority assumptions are stated as above, the 7vPnC data for Cohort 1 were based on GMC results of 1 month after infant series in Group 1 of study B1841008, and 7vPnC data for Cohort 4 were based on GMC results of 1 month after last vaccination of Group 4 in study B1841008. With a 2:1 randomization ratio (13vPnC : Hib vaccine) in Cohort 4, a total of 150 evaluable subjects will provide 100 evaluable subjects with 13vPnC and therefore provide 88.7% power to declare non-inferiority relative to Cohort 1 across all 13 serotypes. With about 15% of randomized subjects nonevaluable in Cohort 4, the total number of subjects to be randomized in the Cohort 4 will be 177.

	Cohort 1(13vPnC)			Cohort 4 (13vPnC)			Difference	Common	Power
Serotype	GMC	GMC (LOG)	SD (LOG)	GMC	GMC (LOG)	SD (LOG)	(LOG)	SD (LOG)	N= 200 (100:100)
7vPnC									
4	6.38	1.853	0.652	9.45	2.246	0.808	0.393	0.760	>0.999
6B	2.88	1.058	0.994	6.36	1.850	1.198	0.792	1.135	>0.999
9V	4.18	1.430	0.826	6.14	1.814	0.838	0.385	0.834	>0.999
14	11.16	2.412	0.953	9.86	2.288	1.382	-0.124	1.257	0.890
18C	4.60	1.526	0.902	7.39	2.000	0.955	0.474	0.938	>0.999
19F	3.60	1.281	1.275	4.53	1.510	1.303	0.230	1.294	0.999
23F	2.45	0.896	1.024	5.64	1.730	1.030	0.834	1.028	>0.999
Additiona	1								
1	7.77	2.050	0.884				0	0.884	>0.999
3	1.68	0.519	0.822				0	0.822	>0.999
5	3.61	1.284	0.842				0	0.842	>0.999
6A	4.76	1.560	0.994				0	0.994	0.998
7F	8.28	2.114	0.778				0	0.778	>0.999
19A	5.1	1.629	0.928				0	0.928	>0.999
Overall									0.887

Table 14.	Power Estimates for Cohort 4, Based on Geometric Mean Concentration
	From Studies B1841008 and B1851015

Abbreviations: GMC = geometric mean concentration; SD = standard deviation. LOG= natural logarithm.

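### SAP 5.1 declares the whole study descriptive and so omits the protocol's non-inferiority rule for the primary immunogenicity objective

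*SAP*

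**What the plan says.** SAP 5.1 makes two statements with no exception for any endpoint: "No formal statistical hypothesis test will be performed as this is a descriptive study and no formal hypotheses were predetermined", and "There are also no formal statistical decision rules for this study and a descriptive estimation approach will be used to assess all study objectives". It then offers point estimates with nominal 95% intervals.

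Protocol 9.2.1 gives the primary immunogenicity objective a success criterion, cohort by cohort: "the primary objective will be achieved if the non-inferiority criterion is met, or the lower bound of the 95% CI on the geometric mean ratio" (last vaccination in Cohort 2, 3 or 4 against the infant series in Cohort 1) "is greater than 0.5 for all 13 serotypes". Protocol 9.5 sets the error rate at 5% two-sided ("or 2.5%, 1-sided test of non-inferiority") with a 2-fold margin, and says that 100 evaluable 13vPnC recipients in Cohort 4 "provide 88.7% power to declare non-inferiority relative to Cohort 1 across all 13 serotypes".

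On changes, the opening of Protocol section 9 allows the SAP to modify the plan but adds that "any major modifications of the primary endpoint definitions or their analyses will also be reflected in a protocol amendment". SAP section 2 repeats that commitment.

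**The concern.** The two governing documents disagree on whether the primary immunogenicity objective can fail. Protocol 1.2 describes the comparison with Cohort 1 as the bridge to efficacy, and the primary report is meant to support licensure. If SAP 5.1 is followed literally, a cohort that misses the bound for one serotype and a cohort that clears all 13 are reported in the same way, as ratios with intervals. Whether anyone then applies the protocol's rule is left open.

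The SAP also conflicts with itself. SAP 7.2 says that all of the type I error is spent on the primary analysis, which has no meaning if no hypothesis is tested.

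**Working it through.** **Where each text uses the word descriptive**

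- Protocol 9.2.2: "All secondary immunogenicity endpoints are descriptive and will be summarized by cohort/group". This covers secondary endpoints only.
- SAP 6.1.2.1: the primary safety endpoints.
- Protocol 9.4 and SAP 7.2: the final study report, in contrast with the primary analysis, which takes all the type I error.
- SAP 5.1: every objective. This is the only place where the word reaches the primary immunogenicity objective.

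**Was the rule withdrawn?** The supplied protocol incorporates Amendment 2 and still carries the rule in 9.2.1 and the sizing in 9.5. SAP section 1 gives consistency with Amendment 2 as the main purpose of the SAP amendment. SAP Table 1 lists added fold-rise analyses, regulator-requested analyses and the additional 280 subjects. It has no entry removing non-inferiority.

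**What the SAP already produces.** SAP 5.2.2 computes the same Student-t intervals on the ln scale as the protocol. SAP 6.1.1.1 reports each GMR and 95% CI against Cohort 1. SAP 4.1 makes the evaluable population primary. Only the margin, the all-13 condition and the conclusion are missing.

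**Is the design built on the rule?** Inputs are the ln differences and common SDs of Protocol Tables 12 to 14, margin ln 2 = 0.693, 100 per group, one-sided 2.5%. The power for one serotype is that of a non-central t test with 198 degrees of freedom and non-centrality

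(ln 2 + difference) / (SD × √(2/100)).

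Cohort 4, serotype 14: (0.693 − 0.124) / (1.257 × 0.1414) = 3.20, power 0.8899 (protocol 0.890). Overall power is the product over the 13 serotypes.

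| Cohort | Product of 13 powers | Protocol | Fails rule (independent serotypes) | Smallest single power | Fails rule (full dependence) |
|---|---|---|---|---|---|
| 2 | 0.9899 | 0.990 | 1.0% | 0.9924 (19F) | 0.8% |
| 3 | 0.9946 | 0.995 | 0.5% | 0.9970 (19F) | 0.3% |
| 4 | 0.8868 | 0.887 | 11.3% | 0.8899 (14) | 11.0% |

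Enrolment also follows: 150/0.85 gives 177 and 100/0.80 gives 125, so 125 + 3 × 177 = 656. The protocol's figures are reproduced. They are powers for a test that SAP 5.1 says is not performed.

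**Would a failure show in the point estimates?** For Cohort 4, the probability that all 13 observed GMRs exceed 0.5 is 0.9993 (normal means). A pass implies that all 13 exceed 0.5, so the probability that all exceed 0.5 and the rule still fails is 0.9993 − 0.8868 = 0.1125. Total failure probability is 1 − 0.8868 = 0.1132, and 0.1125/0.1132 = 99.4%.

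**If evaluable numbers fall short.** The protocol plans 100 per group; 90 and 80 are assumptions. The Cohort 4 product becomes 0.8486 at 90 (15.1% failure) and 0.7967 at 80 (20.3% failure).

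**The case against.** The strongest reply is that little changes in practice. The protocol rule was never amended away, so it remains the prespecified criterion, and every input to it is already in the planned tables. A reader can compare 13 lower bounds with 0.5. The absence of multiplicity adjustment in SAP 5.1 agrees with Protocol 9.5. All of this is correct, and it limits the harm to a missing criterion and conclusion. It does not settle the conflict, because Protocol section 9 lets the SAP modify the protocol and SAP 5.1 says outright that no decision rule exists.

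A second reply is that the failure probabilities are one minus the stated power and are the same whether or not SAP 5.1 is corrected. That also stands. They show how often the omitted rule would matter, not the chance that a failing cohort is presented as a success, which the documents cannot give. The 99% figure is typical of any well-powered non-inferiority comparison.

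Third, part of the front matter is not in the supplied text, and the SAP dates the protocol amendment 19 February 2019 where the protocol's change log dates Amendment 2 07 February 2019. Nothing supplied points to a later amendment that dropped the rule, but the statement that it is unamended is limited to these documents.

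**Conclusion.** The concern holds and must be fixed. SAP 5.1 contradicts Protocol 9.2.1, the sizing in Protocol 9.5 and SAP 7.2 on whether the primary immunogenicity objective has a success criterion. The numerical effect on estimates, intervals, power and enrolment is nil. The effect on inference is that the primary objective, under the SAP as written, ends without a pass or fail for any of the three cohorts. This matters most in Cohort 4, where failure is a realistic outcome under the protocol's assumptions (11.0% to 11.3%, depending on dependence between serotypes). It matters little in Cohorts 2 and 3 (1.0% or less). These figures rest on the GMCs and SDs of Tables 12 to 14 and 100 evaluable subjects per group.

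**What to change.** In SAP 5.1, for the primary immunogenicity endpoint only, replace the text denying hypotheses and decision rules with a reference to Protocol 9.2.1: a cohort succeeds only if all 13 lower 95% bounds of the GMR against Cohort 1 exceed 0.5 in the evaluable population. Add a criterion-met (yes/no) entry per cohort to SAP 6.1.1.1. Keep the descriptive label for safety, secondary endpoints and the final report.

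SAP section 2 says the primary-report analyses have already been run, so record the change in SAP Table 1 as restoring the protocol's prespecified rule, not as adding a hypothesis. The same section keeps the originally enrolled subjects as the primary-report dataset and makes the run that adds the 280 subjects supplemental. One sentence should state what role that run, and the possible repeat with replaced subjects, have for the criterion.

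If a descriptive study was truly intended, the other route is a protocol amendment to 9.2.1, 9.4 and 9.5 together with SAP 7.2. That is the weaker option, because it would drop a prespecified rule after the data have been analysed.

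The cost is SAP wording and one entry in an existing table. No new data or analysis is needed.
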